#### 12.4.4.2. Analyses of Key Secondary Endpoints

The following secondary endpoints will be analyzed using similar statistical methods as the primary endpoint, as appropriate, with details specified in the SAP:

- Number of skills gained or improved at Week 52 (Part 1) as measured by the NSAA
- Change in timed function tests, including the rise from the floor, the 100MWR, time to ascend 4 steps, and the 10MWR from Baseline to Week 52 (Part 1)
- Change in SV95C from Baseline to Week 52 (Part 1)
- Change in PROMIS score in Mobility domain and Upper Extremity Function domain from Baseline to Week 52 (Part 1)

For the secondary endpoint of quantity of delandistrogene moxeparvovec dystrophin protein expression at Week 12 (Part 1) as measured by western blot of biopsied muscle tissue, summary statistics will be provided by treatment group for delandistrogene moxeparvovec dystrophin protein expression at Week 12 (Part 1). A re-randomization test will be performed to compare the endpoint between the 2 treatment groups.

The superiority of delandistrogene moxeparvovec over placebo will be concluded if the test achieves statistical significance based on the multiplicity-adjusted testing procedure that will be specified in the SAP.

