## 6. OBJECTIVES AND ENDPOINTS

| Objectives   | Endpoints  |
|--|--|
| Primary   |  |
| 
 
• To evaluate the effect of delandistrogene moxeparovec on physical function as assessed by the North Star Ambulatory Assessment (NSAA) score
 
  | 
 
• Change in NSAA total score from Baseline to Week 52 (Part 1)
 
   |
| Secondary   |  |
| 
 
• To evaluate the effect of delandistrogene moxeparovec on physical function as assessed by:                             
 
– Number of skills gained or improved on the NSAA
 
 
 
  | 
 
• Number of skills gained or improved at Week 52 (Part 1) as measured by the NSAA
 
  |
| 
 
• To evaluate delandistrogene moxeparovec dystrophin expression from delandistrogene moxeparovec at 12 weeks (Part 1) as measured by western blot of biopsied muscle tissue
 
  | 
 
• Quantity of delandistrogene moxeparovec dystrophin protein expression at Week 12 (Part 1) as measured by western blot
 
  |
| 
 
• To evaluate the effect of delandistrogene moxeparovec on timed function tests as assessed by measuring:                             
 
– Time to rise from the floor
 
– 100-meter walk/run (100MWR)
 
– Time to ascend 4 steps
 
– 10-meter walk/run (10MWR)
 
 
 
 | 
 
• Change in time to rise from the floor from Baseline to Week 52 (Part 1)
 
• Change in time of 100MWR from Baseline to Week 52 (Part 1)
 
• Change in time to ascend 4 steps from Baseline to Week 52 (Part 1)
 
• Change in time of 10MWR from Baseline to Week 52 (Part 1)
 
 |
| 
 
• To evaluate the effect of delandistrogene moxeparovec on stride velocity 95th centile (SV95C) as measured by a wearable device
 
   | 
 
• Change in SV95C from Baseline to Week 52 (Part 1)
 
  |

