### **10.3. Efficacy Assessments**

#### **10.3.1. Functional Assessments**

Every effort must be made to have each subject assessed by the same clinical evaluator for physical functional assessments (NSAA and timed-function tests) throughout the entire study. Functional assessments should be scheduled in the morning and should be the first assessments done during a specific visit. As NSAA is the primary outcome measure, it is to be performed first, followed by the timed-functional tests. Physical functional assessments are to be performed CCI [REDACTED] throughout the study. Every effort should be made for the same assessor to perform the assessments throughout the study for a subject.

If assessments that would impact the primary and/or secondary objectives cannot be performed due to events not reasonably foreseen for a period of time longer than CCI [REDACTED], these assessments may be performed remotely where applicable. The subject should return to the clinic as soon as possible to perform the assessment in person, unless CCI [REDACTED] of the next protocol scheduled assessment as applicable.

Functional assessments will be administered at the time points indicated in Section 2.3.

Refer to the Clinical Evaluator Manual for additional information.

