##### **10.3.1.1.1. Time to Rise from the Floor**

The time to rise from the floor test is part of the NSAA (item 12) and quantifies the time required for the subject to stand in an upright position with arms by sides, starting from the supine position with arms by sides (Henricson 2013). The time required for the subject to complete the task will be recorded during the NSAA administration. As with NSAA, the time to rise from the floor will be collected [CCI].

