##### **10.3.1.2. Time to Ascend 4 Steps**

The timed 4-step test quantifies the time required for the subject to ascend 4 standard steps (each step 6 inches in height) (Bushby 2011). The time required for the subject to climb up 4 standard-sized steps will be recorded.

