## 12. STATISTICAL CONSIDERATIONS

### 12.1. Statistical Hypotheses

For the primary efficacy endpoint of change in NSAA total score from Baseline to Week 52 (Part 1), the null hypothesis is that the population means for the 2 treatments are equal and the alternative hypothesis is that the population means for the 2 treatments are not equal. Even though the alternative hypothesis is 2-sided, only superiority of delandistrogene moxeparvec over placebo will be of interest.

The statistical hypotheses for secondary efficacy endpoints can be stated in a similar manner as those for change in NSAA total score from Baseline to Week 52 (Part 1).

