### 12.3. Analysis Populations

For purposes of statistical analyses, the following analysis populations are defined:

| Population                      | Description   |
|---------------------------------|---|
| Intent-to-Treat (ITT)           | All randomized subjects (not including those enrolled under a regional addendum), with treatment group designated according to randomization.   |
| Modified Intent-to-Treat (mITT) | All randomized subjects who receive study treatment (not including those enrolled under a regional addendum), with treatment group designated according to randomization. The mITT population will be the analysis population for efficacy endpoints. |
| Safety                          | All subjects who received study treatment (not including those enrolled under a regional addendum), with treatment group designated according to the treatment that they actually received.   |

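### Does the plan need a stated value for a boy who can no longer complete a timed function test?

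*Combined protocol and SAP*

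**What the plan says.** Section 6 lists four timed secondary endpoints (rise from the floor, 100-metre walk/run, 4 steps, 10-metre walk/run), each as the change in time from Baseline to Week 52 of Part 1. Section 12.1 sets the primary hypothesis on means ("the null hypothesis is that the population means for the 2 treatments are equal") and adds: "The statistical hypotheses for secondary efficacy endpoints can be stated in a similar manner". Section 12.3 fixes whose data count: "The mITT population will be the analysis population for efficacy endpoints". The mITT set is the randomized and dosed boys, without those enrolled under a regional addendum.

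For measurement, section 10.3.1.1.1 says "The time required for the subject to complete the task will be recorded during the NSAA administration" and section 10.3.1.2 says "The time required for the subject to climb up 4 standard-sized steps will be recorded". Neither covers an attempt that is not completed. Section 10.3.1 adds "Refer to the Clinical Evaluator Manual for additional information".

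For analysis, section 12.4.4.2 says "The following secondary endpoints will be analyzed using similar statistical methods as the primary endpoint, as appropriate, with details specified in the SAP". The primary method in section 12.4.4.1 is a mixed model for repeated measures under missing at random. Section 12.4 calls itself a summary and commits to a SAP finalized before database lock and unblinding. The text reviewed here contains no SAP section and no manual. Parts of sections 8.1 (inclusion criteria 4 and 5), 10.3.1.1.1, 10.3.1.1.2 and 12.4.4.1 are blacked out.

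**The concern.** A boy who tries to rise from the floor at Week 52 and cannot is in the mITT population but has no time. The NSAA scores inability as 0 (section 10.3.1.1), so the primary endpoint covers him. The timed tests have no readable counterpart. He could be left missing, given a fixed high time, given the worst observed time, or analysed as velocity with 0.

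These choices are not equivalent on a scale in seconds, where a single large value adds both mean shift and variance. Section 12.4.4.2 draws superiority conclusions from the secondary endpoints, and section 12.4.4 places some of them under familywise error control. The readable commitment to test departures from missing at random names the primary analysis only. If one or two boys could decide a test, a reader would want the rule fixed in advance.

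**Working it through.** **1. The plan's own figure.** About 120 boys, 1:1, so about 60 per arm. The effect, SD and power behind this are blacked out, so it cannot be reproduced. What 60 per arm can detect at two-sided 0.05 is (1.960 + z) × √(2/60), with √(2/60) = 0.1826:
- 80% power: (1.960 + 0.842) × 0.1826 = 0.51 SD
- 90% power: (1.960 + 1.282) × 0.1826 = 0.59 SD
- 95% power: (1.960 + 1.645) × 0.1826 = 0.66 SD

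**2. Hand calculation.** One boy scored L seconds above his baseline, instead of being left out, moves his arm mean by about L/60. With an assumed baseline of 4 s:
- 30 s: 26/60 = 0.43 s
- 15 s: 11/60 = 0.18 s
- 9.7 s (the slowest time that can be recorded in step 3): 5.7/60 = 0.10 s

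The size is set by the assigned time.

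**3. Mixed-model simulation (3000 trials per scenario).** Only the arm size comes from the protocol. The rest is assumed: median baseline 4 s; true difference about −0.80 s; visits at Weeks 12, 24, 36 and 52; no mean placebo drift; a boy is unable once his time passes 9.7 s, and stays so. This gives 3.0% unable on placebo and 1.1% on drug, on average 2.4 boys of 120.

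| Rule for unable boys | Difference (s) | Power | Conclusion differs from left missing |
|---|---|---|---|
| Left missing | −0.73 | 83.8% | – |
| Worst observed time | −0.77 | 84.4% | 5% |
| 12 s | not given | 81.4% | not given |
| Velocity, unable = 0 | other scale | 83.3% | not given |
| 15 s | −0.87 | 76.3% | 14% |
| 20 s | −0.96 | 66.5% | 24% |
| 30 s | −1.14 | 50.8% | 38% |

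If unable boys are left missing, the difference shrinks by 4.9, 8.2, 14.4 and 20.3% at 1.3, 3.0, 6.4 and 11.1% placebo loss. A second input set with less noise gave 5.3, 9.2 and 14.4% at 2.9, 5.9 and 10.8%. A separate check gave less, so the range is about 2 to 9% at 3% loss and 8 to 20% at 11%. With no treatment effect and 3% unable per arm, rejection was 3.8 to 5.0% whichever single rule was used.

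**4. Second simulation (t-test on Week 52 change, 2000 runs).** Assumed: baseline 4.0 s, benefit 0.6 s, SD of change 1.1 s, the slowest boys unable. Entries are estimated benefit / chance of a significant win.

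| Unable, placebo v drug | Left out | 15 s | 30 s |
|---|---|---|---|
| 0 v 0 | 0.54 s / 81–82% | same | same |
| 2 v 0 | 0.50 s / 74–75% | 0.80 s / 90% | 1.30 s / 74% |
| 3 v 1 | 0.50 s / 77% | 0.81 s / 70% | 1.31 s / 5% |
| 0 v 2 | 0.61 s / 89–91% | 0.28 s / 6% | −0.21 s / 0% |

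At 3 v 1, worst observed time gave 82% and worst rank 81%.

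**5. Reading.** Leaving boys missing, worst observed, 12 s and velocity with 0 give power of 81.4 to 84.4% in step 3. The large swings come from fixed times of 15 s and above, at least 15/9.7 = 1.5 times the slowest time that could be recorded in that scenario.

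**The case for a change.** The strongest case for a change is that inability is foreseeable and silence is not neutral. Section 5.1 names rising and stair climbing as abilities most patients lose by 8 years. Boys enter up to just under 8, and section 10.3.6.1 provides for those who reach 8 on study. Treating loss of function like a missed visit is a weak default. Even worst-observed scoring changed the conclusion in 5% of trials in step 3. A simpler Week 52 ANCOVA on the same assumed inputs gave 11% for worst observed and 37% for 30 s.

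It stands that no readable section states the rule, and that a large fixed time would need justification. It also stands that leaving boys out need not be conservative. With none unable on placebo and two on drug, the estimate rose to 0.61 s against 0.54 s with nobody unable. In the t-test check with no benefit (SD 1.5 s), that split gave a false win in 5.7 to 5.9% of runs, against a one-sided 2.5%; two on placebo and none on drug gave 1.1%. Without a drug effect, neither direction is favoured, and the mixed-model simulation over such imbalances stayed at 3.8 to 5.0%.

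The rest is weaker. The definitions do not conflict: mITT says whose data are analysed, not that every boy has a value at every visit, and a mixed model estimates a mean change with values missing. It also uses a boy's earlier, slowing times. The statement in section 5.1 concerns boys without glucocorticoids, whereas section 5.4 puts every subject on corticosteroids. In a rebuild of the step 3 inputs, only about 30% of the unable placebo boys had an underlying Week 52 time above the limit (mean 8.9 s), so much of the simulated inability was visit noise later scored at up to 30 s. Choosing a rule after seeing results is the remaining risk, and section 12.4 already requires the SAP before unblinding.

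**Conclusion.** No change follows. This is an unstated detail in a protocol summary, of a kind that the SAP or the test manual normally settles, and it may already be settled there or under redaction. The readable default shrinks the difference by about 2 to 9% at roughly 3% placebo loss, with no type I error inflation when inability is equally likely in both arms. Other rules near the observed range give much the same power. Large dependence mainly needs a fixed time of 15 s or more, which nothing readable proposes. A reason field, counts of unable boys and extra sensitivity analyses would inform a reader but leave the planned test as it is.

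The conclusion rests on assumed effects, spreads and loss rates. At around 11% loss the shrinkage would be 8 to 20%; with nobody unable it would be zero. It also rests on the SAP being final before unblinding, as section 12.4 commits.

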#### 12.4.5. Safety Analyses

##### 12.4.5.1. Adverse Events

All safety analyses will be based on the safety population.

Adverse events will be coded using the Medical Dictionary for Regulatory Activities. A TEAE will be defined as an AE that emerges during treatment, having been absent pre-treatment, or worsens relative to the pretreatment state. A drug-related TEAE will be defined as a TEAE that the Investigator considers related to study drug.

Treatment-emergent adverse events and drug-related TEAEs will be summarized separately by treatment group by the number and percentage of subjects who reported TEAEs. Safety analyses for each study period will use all visits up through the last scheduled visit in the prior study period as baseline. For each subject and TEAE, the maximum severity for the MedDRA level being displayed (preferred term, High Level Term, or system organ class [SOC]) is the

maximum post-baseline severity observed from all associated terms mapping to that MedDRA level.

Serious adverse events, and treatment-emergent SAEs separately, will be summarized by treatment group.

#### **12.4.5.2. Other Safety Assessments**

Descriptive statistics for ECG, vital signs, immunogenicity, and safety laboratory parameters will be generated. Summary statistics for each parameter at specific time points, as well as the change from Baseline to that time point (if applicable), will also be displayed. All safety data will be presented in the data listings.

#### **12.5. Interim Analysis**

The primary analysis of the study will be performed after all subjects have completed Part 1 or have withdrawn early from Part 1. No interim analysis is planned prior to the completion of Part 1.

#### **12.6. Data Monitoring Committee**

A program-wide independent Data Monitoring Committee (DMC) will monitor safety, efficacy, data quality, and the integrity of study. The activities and composition of this committee are outlined in the DMC Charter.

## **13. DATA COLLECTION, QUALITY ASSURANCE, AND MANAGEMENT**

### **13.1. Study Monitoring**

Before an investigational site can enter a subject into the study, a representative of the Sponsor will visit the investigational study site to:

- Determine the adequacy of the facilities
- Discuss with the Investigator(s) and other personnel their responsibilities with regard to protocol adherence, and the responsibilities of the Sponsor or its representatives. This will be documented in a Clinical Study Agreement between the Sponsor and the Investigator.

The Investigator(s)/institution(s) agree to provide direct access to source data/documents (including electronic records, unless prohibited by local regulations) for study-related monitoring, audits, IRB/IEC review, and regulatory inspections.

During the study, a monitor from the Sponsor or representative will have regular contacts with the investigational site, for the following:

1. Provide information and support to the Investigator(s)
2. Confirm that facilities remain acceptable
3. Confirm that the investigational team is adhering to the protocol, that data are being accurately recorded in the case report forms, and that study drug accountability checks are being performed
4. Perform source data verification. This includes a comparison of the data in the case report forms with the subject's medical records at the hospital or practice, and other records relevant to the study. This will require direct access to all original records for each subject (eg, clinic charts).
5. Record and report any protocol deviations not previously sent to the Sponsor.
6. Confirm AEs and SAEs have been properly documented on case report forms and confirm any SAEs have been forwarded to the Sponsor and those SAEs that met criteria for reporting have been forwarded to the IRB/IEC as required.

The monitor will be available between visits if the Investigator(s) or other staff need information or advice.

### **13.2. Recording of Data**

Clinical data for this study will be captured in an electronic format. The Investigator, or personnel delegated by the Investigator, will perform primary data collection/perform assessments based on the protocol design and captured in source documentation. Source documents are filed at the Investigator's site. All required study information must be recorded on the appropriate eCRF screens/forms. Data entered in the eCRF that are transcribed from source documents must be consistent with the source documents. All data must be carefully entered in a timely fashion to permit meaningful interpretation and study oversight.

### **13.3. Quality Assurance**

The eCRFs will be reviewed at regular intervals by a Clinical Monitor from the Sponsor or a representative of the Sponsor per the agreed-upon Clinical Monitoring Plan against the source documentation for identification and clarification of any discrepancies. The Investigator must maintain accurate documentation (source data) that supports the information entered in the eCRF. Automated and manual quality checks will be in place to identify discrepancies, such as missing data, protocol deviations, out of range data, other data inconsistencies, and compliance. Requests for data clarification or correction will be documented as electronic queries within the eCRF and for the Investigator or site staff to resolve. All changes to the eCRFs will be tracked in an electronic audit trail. Investigator site files will be reviewed for compliance throughout the study.

Audits may be carried out by the Sponsor's representatives, and inspections may be performed by IRBs/IECs or regulatory authorities before, during, or after the study. The Investigator will allow and assist the Sponsor's representatives and any regulatory agency to have direct access to all study records, eCRFs, subject medical records, and other source documentation, study drug dispensing records and storage area, study facilities, and any other source documentation.

The Investigator must make study files and data accessible to the Study Monitor, to other authorized representatives of the Sponsor, and to the appropriate regulatory authority inspectors.

### **13.4. Retention of Study Documents**

At CSR completion, all eCRF data for an individual site will be provided via electronic media to the Investigator for retention in the Investigator site files.

The length of storage of study documents varies by country and stage of clinical development in any region in the world. Therefore, no study documents, including subject records and other source data, will be destroyed, or moved to a new location without prior written approval from the Sponsor.

If the Investigator relocates, retires, or withdraws from the clinical study for any reason, all records that are required to be maintained for the study are to be transferred to an agreed-upon designee.

If offsite archiving is used, all records must be retrieved and made available for review at the time of an audit or regulatory authority inspection.

## **14. ETHICS AND OTHER SPECIAL REQUIREMENTS**

It is the responsibility of both the Sponsor and the Investigator(s) to ensure that this clinical study will be conducted in accordance with the ethical and scientific principles governing clinical research as set out in the Declaration of Helsinki, GCP Guidelines described in the ICH E6 (R2) and 21 Code of Federal Regulations parts 50, 54, 56, and 312; and applicable national regulations and directives such as EU Clinical Practice Directive 2005/28/EC, Regulation EU No 536/2014, Japanese GCP Regulation, and other applicable regulatory requirements. The clinical study will be conducted in compliance with Pharmaceutical and Medical Device Act, and the Clinical Study Protocol.

### **14.1. Institutional and Ethics Review**

Before study initiation, the protocol, Investigator's Brochure, informed consent/assent form, parental ICF (for parents/legal guardians), and other relevant documents (as applicable) will be submitted, reviewed, and approved by the appropriate IRB/IEC and regulatory authority. Amendments to the protocol and all substantial changes to the study documentation will require IRB/IEC and regulatory authority review and approval before implementation of changes made to the study design, except for changes necessary to eliminate an immediate hazard to study subjects.

The Investigator will promptly notify the IRB/IEC and Sponsor of any SAEs or of any other information that might affect the safe use of the study drug during the study according to the IRB/IEC requirements. The IRB approvals/IEC positive opinions and regulatory authorities' approvals must be sent to the Sponsor (or designee) before initiation of the study or before an amendment is instituted.

All correspondence with the IRB/IEC and regulatory authorities must be retained within the study regulatory files and made available for inspection.

### **14.2. Informed Consent and Assent**

Informed consent and assent from each subject and/or parent/legal guardian must be obtained before any study-specific evaluations are performed. A copy of the signed informed consent (and assent) form will be given to the subject and/or parent/legal guardian; the Investigator will retain the original copies of these documents.

The informed consent/assent documents, as prepared by the Sponsor (or designee), must be reviewed and approved by the IRB/IEC and regulatory authorities, as applicable, before initiation of the study. The informed consent document must contain the basic required elements of consent and additional elements, as applicable, as specified in ICH GCP E6 (R2). In the event of an update to the ICF/assent(s), subjects must be re-consented to the most current IRB/IEC-approved version of the ICF/assent(s) prior to continuation of their participation in the study.

